6.0 GENERAL DATA DERIVATIONS

6.1 Study Day Calculation

Study Day 1 is the day of the S8 Sinus Implant placement at the baseline/procedure. Study Day is calculated relative to Study Day 1 and appears in the listings where applicable.

If the date of event is on or after the date of the S8 Sinus Implant placement at the baseline/procedure, Study Day is calculated as:

$$\text{Study Day} = \text{Date of event} - \text{Date of procedure} + 1$$

Otherwise,

$$\text{Study Day} = \text{Date of event} - \text{Date of procedure}$$

6.2 Baseline

The baseline is defined as the last observation recorded prior to the first attempt of the S8 Sinus Implant placement.

6.3 Change from Baseline Calculation

Change from baseline is calculated as:

$$\text{Change from Baseline} = \text{Follow-Up Result} - \text{Baseline Result}$$

A negative value corresponds to a decrease (improvement), whereas a positive value corresponds to an increase (worsening).

6.4 Study Visits

Subjects return for 7 follow-up visits at Days 30, 60, 90, 120, 150, 180 and 365 (end of study). Data from protocol-specified visits (i.e., as reported in the case report form or CRF) are used in the summary tables and data listings. If unscheduled visits occur during which high-dose steroids are prescribed (and after which high-dose steroids are taken by the subject), data from those visits will be used as last observations carried forward in statistical analyses (see Section 7.3 Medical or Surgical Interventions).

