11.3 Follow-Up Phase

The follow-up period begins immediately post-procedure (once the patient exits the clinic). Each subject will return for up to 7 follow-up visits (*see Section 5 Study Flow Diagram and Section 6 Schedule of Assessments*).

- Day 30 (\pm 7 days)
- Day 60 (\pm 7 days)
- Day 90 (\pm 7 days) – implant removal & repeat implant placement
- Day 120 (\pm 7 days)
- Day 150 (\pm 7 days)
- Day 180 (\pm 14 days) – implant removal, as applicable
- Day 365 (\pm 14 days)

The protocol-required follow-up assessment at each visit through Day 180 will consist of:

- Nasal obstruction/congestion questionnaire,
- SNOT-22 questionnaire, and
- Endoscopic grading and video recording.

Repeat implant placement procedure at Day 90

At the Day 90 follow-up visit, subjects with ethmoid sinuses with polyps (grade ≥ 1) will undergo repeat implant placement unilaterally or bilaterally. Repeat implant placement must not be performed in the ethmoid sinuses with no nasal polyps (grade < 1). All implants placed at Day 90 must be removed at Day 180 or may be removed earlier at the investigator's discretion.

If polypectomy is performed at the Day 90 follow-up visit, polyp grading must be done after polypectomy to qualify a given subject for repeat placement of the S8 Sinus Implant.

Note: The assessment of symptoms and pregnancy testing must be performed before repeat implant placement procedure.

Unscheduled visits

Subjects may come in for additional unscheduled office visits if necessary. Circumstances that may warrant additional visits include but are not limited to:

- Worsening of sinus symptoms,
- Sinus-related adverse events requiring medical evaluation, and/or
- Implant migration

The assessment at an unscheduled visit will consist of:

- Nasal obstruction/congestion questionnaire,
- SNOT-22 questionnaire, and
- Endoscopic grading and video recording.

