7.3 Medical or Surgical Interventions

Since high-dose steroids (e.g., oral, parenteral, injection, budesonide or other sinus steroid irrigations, rinses or drops, nebulized steroids administered nasally) or surgical intervention may confound the efficacy measures, the following method will be applied to the analyses in cases where such interventions are performed:

- If a subject initiates high-dose steroids (see Clinical Study Protocol Appendix A for a list of medications considered as high-dose steroids) or undergoes polypectomy or revision ESS for chronic sinusitis conditions attributable to the ethmoid sinus during the study, this represents treatment failure.
- For subjects with interventions for treatment failure occurring at any time point through Day 180 (regardless of receiving repeat implant placement at Day 90), the last available scores for Nasal Obstruction/Congestion, SNOT-22, and endoscopic measures prior to interventions will be carried forward to all time points through Day 180 or the last follow-up visit.

No other data imputation rules will be applied in the planned statistical analyses. All efficacy endpoints will be presented as intervention-adjusted values.

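### SAP 6.4 and 7.3 conflict on which score is carried forward after surgical rescue: 6.4 admits unscheduled-visit scores only for high-dose steroids, 7.3 does not limit the visit type

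*SAP*

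**What the plan says.** SAP 6.4 (Study Visits) sets the default: "Data from protocol-specified visits (i.e., as reported in the case report form or CRF) are used in the summary tables and data listings". It then makes a single exception. That sentence begins "If unscheduled visits occur during which high-dose steroids are prescribed", adds that the subject must go on to take them, and says that "data from those visits will be used as last observations carried forward in statistical analyses". It refers the reader to SAP 7.3. It does not mention surgery.

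SAP 7.3 (Medical or Surgical Interventions) puts surgery on the same footing as high-dose steroids: if a subject "undergoes polypectomy or revision ESS for chronic sinusitis conditions attributable to the ethmoid sinus during the study, this represents treatment failure". For any such intervention through Day 180, "the last available scores for Nasal Obstruction/Congestion, SNOT-22, and endoscopic measures prior to interventions will be carried forward" to the later time points. The type of visit is not stated. The section adds "No other data imputation rules will be applied in the planned statistical analyses" and "All efficacy endpoints will be presented as intervention-adjusted values".

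Protocol 11.3 lists worsening sinus symptoms among the reasons for an unscheduled visit. The sentence starting "The assessment at an unscheduled visit will consist of" is followed by the congestion questionnaire, SNOT-22 and endoscopic grading. A score from an unscheduled visit before surgery should therefore normally exist.

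**The concern.** The SAP does not say whether the scores that 7.3 calls available are limited by the visit rule in 6.4. A programmer who follows 6.4 drops the unscheduled score that preceded surgery and carries forward the previous scheduled one. A programmer who follows 7.3 keeps it. Both could say that they followed the plan.

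The difference is not neutral. If the subject came in because symptoms had worsened, the dropped score is the worse one. Two subjects with the same course and the same unscheduled visit would be analysed differently because one took steroids and the other had surgery, although 7.3 calls both treatment failures. The 6.4 reading flatters the implant in the efficacy means. It can also do so in the responder rates and in the Day 90 and Day 180 proportions indicated for repeat sinus surgery (SAP 7.4). Because 6.4 applies its visit rule to listings as well as tables, the dropped score might not be displayed anywhere.

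**Working it through.** **Figures in the plan.** The plan gives no figure for this point. The sample size rests on clinical judgment (Protocol 16.1, SAP 7.2). Its only arithmetic reproduces (2 × 50 = 100 baseline sinuses; 100 + 85 = 185 procedures) but has no bearing here.

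**The two rules side by side.**

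| Rescue following an unscheduled visit | SAP 6.4 read literally | SAP 7.3 read literally |
|---|---|---|
| High-dose steroids prescribed there and taken | unscheduled score used | unscheduled score used |
| Polypectomy or revision ESS, no steroids | previous scheduled score used | unscheduled score used |

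The rules differ only in the second row. If 7.3 by itself admitted unscheduled scores, the exception in 6.4 would not be needed. Its presence is evidence for the restrictive reading, but it does not settle the matter.

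**One subject (assumed scores).** Bilateral polyp grade is 5.5 at baseline, 3.0 at Day 60 and 5.5 at a later unscheduled visit before Day 90. Polypectomy follows and no steroids are taken.

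- Under 6.4, 3.0 is carried forward. The change is 3.0 − 5.5 = −2.5 at Days 90 to 180, so the subject is a responder at both the 1.0-point and 2.0-point cut-offs in SAP 7.4.
- Under 7.3, 5.5 is carried forward. The change is 5.5 − 5.5 = 0.0, so the subject is a non-responder at both.
- Had the same visit led to steroids that were taken, 6.4 itself would use 5.5.

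**Cohort effect.** Inputs:

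- N = 50 (SAP 7.2), taking all 50 to contribute at the time point.
- k = number of affected subjects. Not in the documents; assumed 1 to 5.
- d = worsening in bilateral grade since the last scheduled visit. Not in the documents; assumed 0.5 to 3 points on the 0 to 8 scale.

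Shift in mean change = k × d / N:

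| k | d = 0.5 | d = 1 | d = 2 | d = 3 |
|---|---|---|---|---|
| 1 | 0.01 | 0.02 | 0.04 | 0.06 |
| 2 | 0.02 | 0.04 | 0.08 | 0.12 |
| 3 | 0.03 | 0.06 | 0.12 | 0.18 |
| 5 | 0.05 | 0.10 | 0.20 | 0.30 |

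Largest possible shift in a responder rate = k / N: 1/50 = 2 percentage points up to 5/50 = 10. This takes responder rates to be computed from the carried-forward scores, and it is reached only if every affected subject crosses the cut-off.

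**The case against.** The strongest reply is that 7.3 is the operative imputation rule. It names surgery, it does not restrict the scores to scheduled visits, and 6.4 defers to it by cross-reference. On that reading the unscheduled pre-surgery score is used and nothing is lost. This stands to the extent that a reader might infer from 6.4 that the plan definitely carries forward the older score. The documents do not support that: 6.4 does not say that its steroid exception overrides 7.3. What remains is a conflict that the SAP does not resolve.

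The trigger is also narrow. Surgery must be for ethmoid disease and take place by Day 180. It must follow an unscheduled visit that did not lead to steroids being taken, and the scores there must be worse than at the last scheduled visit, with those visits about 30 days apart. Surgery decided at a scheduled visit need not be affected. Protocol 13.2 also allows surgery for persistent polyposis, where the older score need not be better. All of this stands.

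A reader might further infer that every efficacy summary is biased and that nothing else in the report would show it. Neither follows. A threshold summary changes only for a subject who crosses the cut-off. Interventions received, including polypectomy and repeat ESS, are reported through Day 365 (SAP 4.3 and 7.4), so the number of surgical rescues will be visible and the effect can be bounded. That table does not recover the dropped scores.

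**Conclusion.** The point holds as an unresolved conflict between SAP 6.4 and 7.3. Under the literal reading of 6.4, equal failures are treated unequally, and the error favours the implant whenever the subject worsened between the last scheduled visit and surgery.

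The size is known only under assumption. With 1 to 5 affected subjects and 0.5 to 3 points of worsening, it runs from a negligible 0.01 to 0.30 points in mean bilateral polyp grade, with a ceiling of 2 to 10 percentage points on a responder rate. If no subject follows this path, the effect is zero. A larger figure would need a rescue rate or a degree of worsening that the documents do not give.

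The stakes are moderate. The objective is safety, the trial is single-arm and open-label, the continuous efficacy measures are summarised descriptively, and no efficacy hypothesis or success criterion depends on this choice. The adverse event analysis is untouched. It is still worth correcting, because a stated rule can give a favourably biased result and the data to avoid that are already collected.

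**What to change.** State in SAP 7.3 that, for every treatment-failure intervention actually received (high-dose steroids, polypectomy or revision ESS), the value carried forward for each measure is the last score recorded before the intervention, at any scheduled or unscheduled visit. Reword the exception in SAP 6.4 to match, or replace it with a reference to that rule.

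Two details of this wording matter. Tying the rule to interventions actually received keeps the safeguard in 6.4 that steroids must have been taken, and it excludes surgery that was planned but never done. Tying it to the last score before the intervention, rather than to the visit at which surgery was decided, picks the right value when another visit falls between decision and surgery.

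The cost is one sentence in 7.3 and a matching edit in 6.4, with no new data and no change to how subjects are managed. The downside is that reported efficacy may become slightly less favourable. The change should be made before database lock, because SAP 6.5 classes analyses designed after lock as post hoc.

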6.5 General Statistical Considerations

All analyses described in this plan are considered *a priori* analyses, as they have been defined prior to locking the database. All other analyses, designed subsequently to the database lock, will represent *post hoc* analyses and will be considered as exploratory. Any *post hoc* analyses will be clearly identified in the clinical study report.

6.6 General Statistical Procedures

Statistical summaries and confidence intervals (CI) are generated using SAS[®] software, version 9.4 or higher. Descriptive statistics are provided for all summarized data by displaying the mean, standard deviation (SD), median, minimum and maximum for continuous data, and the count and percentage for categorical data. Unless stated otherwise, a two-sided 95% CI is calculated when a CI is presented. A p-value < 0.05 is considered as statistically significant.

7.0 STATISTICAL ANALYSES

7.1 Demographics and Baseline Clinical Characteristics

Demographic data (i.e., age, gender, race) and baseline clinical characteristics (i.e., number of prior endoscopic sinus surgery (ESS), days since last ESS, symptoms that have been present for ≥ 12 weeks prior to baseline, history of smoking, current status of asthma and allergic rhinitis diagnosed by physician, aspirin intolerance or aspirin allergy, and allergies) will be presented. Baseline clinical characteristics including polyp grade and Nasal Obstruction/Congestion scores

will also be summarized.

7.2 Sample Size

The 50-patient sample size was selected based on clinical judgment. In the RESOLVE II study, ~90% of sinuses had polyp grades ≥ 1 at Day 90. From this data, it is expected that of the 100 sinuses undergoing implant placement at baseline, greater than 85 sinuses would undergo repeat placements at Day 90. Therefore, a sample of 50 subjects will provide safety data on up to 185 implant procedures (100 implants at baseline; 85 implants at Day 90), which is deemed to be a large enough sample to detect potential additional implant-related adverse events associated with recurrent use of the implant.

7.3 Medical or Surgical Interventions

Since high-dose steroids (e.g., oral, parenteral, injection, budesonide or other sinus steroid irrigations, rinses or drops, nebulized steroids administered nasally) or surgical intervention may confound the efficacy measures, the following method will be applied to the analyses in cases where such interventions are performed:

- If a subject initiates high-dose steroids (see Clinical Study Protocol Appendix A for a list of medications considered as high-dose steroids) or undergoes polypectomy or revision ESS for chronic sinusitis conditions attributable to the ethmoid sinus during the study, this represents treatment failure.
- For subjects with interventions for treatment failure occurring at any time point through Day 180 (regardless of receiving repeat implant placement at Day 90), the last available scores for Nasal Obstruction/Congestion, SNOT-22, and endoscopic measures prior to interventions will be carried forward to all time points through Day 180 or the last follow-up visit.

No other data imputation rules will be applied in the planned statistical analyses. All efficacy endpoints will be presented as intervention-adjusted values.

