4.3 Other Endpoints

Implant delivery success rate

Percentage of successful deployments of the S8 Sinus Implant to the target site per total number of sinuses attempted during the baseline and repeat placement procedures.

Interventions received

Proportion of subjects who received interventions (i.e., steroids or antibiotics for ethmoid sinus obstruction or for other reasons, polypectomy, repeat endoscopic sinus surgery) through Day 365.

Responder rates: Proportion of subjects who were responders as defined by nasal obstruction/congestion and bilateral polyp grade.

Indicated for repeat endoscopic sinus surgery (RESS) based on clinical data: Proportion of subjects who are indicated for RESS based on nasal obstruction/congestion score ≥ 2 and polyp grade ≥ 2 on each side.

Implant status: Proportion of sinuses with implant status of present, absent, or removed.

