- Responder rates: Proportion of subjects with clinically meaningful improvement from baseline in nasal obstruction/congestion score and/or bilateral polyp grade at each time-point (Days 30, 60, 90, 120, 150, 180) will be presented. Responders include subjects with:
 - Nasal obstruction/congestion score, ≥ 1.0 -point reduction from baseline
 - Nasal obstruction/congestion score, ≥ 2.0 -point reduction from baseline
 - Nasal obstruction/congestion score < 2.0
 - Bilateral polyp grade, ≥ 1.0 -point reduction from baseline
 - Bilateral polyp grade, ≥ 2.0 -point reduction from baseline
 - Polyp grade < 2 on each side
 - Nasal obstruction/congestion score ≥ 0.5 and bilateral polyp grade, ≥ 1.0 -point reduction
 - Nasal obstruction/congestion score ≥ 0.5 and bilateral polyp grade, ≥ 2.0 -point reduction
 - Nasal obstruction/congestion score ≥ 1.0 and bilateral polyp grade, ≥ 1.0 -point reduction
 - Nasal obstruction/congestion score ≥ 1.0 and bilateral polyp grade, ≥ 2.0 -point reduction
- Indicated for repeat endoscopic sinus surgery (RESS) based on clinical data: Proportion of subjects who are indicated for RESS based on nasal obstruction/congestion score ≥ 2 and polyp grade ≥ 2 on each side at Day 90 and at Day 180.
- Implant status: Proportion of subjects with implant status of present, absent, or removed, as assessed at each time-point (Days 30, 60, 90, 120, 150, 180).

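### Rescued subjects that the SAP calls treatment failures can still be counted as responders, and the responder row for an obstruction score below 2.0 requires no improvement

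*SAP*

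**What the plan says.** SAP 7.3 covers subjects who start high-dose steroids, or undergo polypectomy or revision sinus surgery, for sinusitis attributable to the ethmoid sinus. It states that "this represents treatment failure". For such subjects the last available obstruction/congestion, SNOT-22 and endoscopic scores "prior to interventions will be carried forward to all time points through Day 180 or the last follow-up visit". It adds: "No other data imputation rules will be applied in the planned statistical analyses".

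SAP 4.3 lists the responder endpoint: "Proportion of subjects who were responders as defined by nasal obstruction/congestion and bilateral polyp grade". SAP 7.4 introduces it as "Proportion of subjects with clinically meaningful improvement from baseline in nasal obstruction/congestion score and/or bilateral polyp grade at each time-point" and gives ten rows, each defined by score thresholds. None mentions rescue or treatment failure. One row reads, in full, "Nasal obstruction/congestion score < 2.0".

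On entry, Protocol 10.2 (inclusion f) requires polyp grade 2 or more on each side. No criterion sets a minimum obstruction/congestion score. The diagnosis in Protocol 3 needs any two of four symptoms, so obstruction need not be one of them.

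**The concern.** (a) The failure label does not reach the responder rows. A subject who improved partly, was still symptomatic enough to need rescue, and had a qualifying score just before it is called a treatment failure in one section. The same subject is reported under clinically meaningful improvement in another, at every later visit through Day 180.

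(b) The below-2.0 row measures status at the visit, not change. Under its heading, a subject with mild or no obstruction throughout is presented as having benefited.

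The trial has a single arm, so no control group would reveal either effect. A reader of the tables would take each rate as the proportion helped by the implant without rescue. At stake is the interpretation of descriptive responder rates; the adverse-event analyses do not use them.

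**Working it through.** **Plan figures.** The plan states no expected responder rate, rescue rate or baseline obstruction distribution, so there is no plan figure to reproduce for this point. The only design figure is 185 implant procedures (SAP 7.2): 50 × 2 + 85 = 185, which reproduces but is not needed here. The input used is N = 50, so one subject = 1/50 = 2 points.

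**(a) Carry-forward applied to the responder rows.** Inputs: the SAP 7.3 rule, the SAP 7.4 thresholds and the scales in Protocol 3. Once a score is carried forward, the change from baseline is fixed at all later visits through Day 180.

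| Measure | Baseline | Last before rescue | Reduction | Row met after rescue |
|---|---|---|---|---|
| Obstruction | 3 | 2 | 1 | 1.0-point reduction |
| Obstruction | 2 | 1 | 1 | 1.0-point reduction, and below 2.0 |
| Bilateral polyp grade | 3 + 3 = 6 | 2.5 + 2.5 = 5 | 1 | 1.0-point reduction |

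Size: if k subjects are failures with a qualifying carried score, counting them as non-responders lowers the rate by k/50. Assume, for illustration only, a printed rate of 30/50. Intervals are exact (Clopper-Pearson), the method that SAP 7.4 names.

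| k (assumed) | Rate | 95% CI |
|---|---|---|
| 0 | 30/50 = 60.0% | 45.2 to 73.6 |
| 1 | 29/50 = 58.0% | 43.2 to 71.8 |
| 3 | 27/50 = 54.0% | 39.3 to 68.2 |
| 5 | 25/50 = 50.0% | 35.5 to 64.5 |

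**(b) The below-2.0 row.** On the whole-number 0 to 3 scale, 4 baseline values × 2 follow-up values (0 or 1) = 8 pairs satisfy the row. Three show no improvement: 0 to 0, 1 to 1, and 0 to 1, which is a worsening. If m subjects start below 2 and stay there, the row cannot fall below m/50 even when nobody improves.

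| m (assumed) | Floor of the row | Denominator if baseline 2 or more is required |
|---|---|---|
| 0 | 0% | 50 |
| 2 | 4% | 48 |
| 5 | 10% | 45 |
| 10 | 20% | 40 |

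The parallel row on polyp grade below 2 on each side does not share this fault where the analysis baseline meets the entry criteria. Eligible grades are 2 to 3.5, and the highest grade below 2 is 1.5. The row therefore needs a drop of at least 2 − 1.5 = 0.5 per side, or 1.0 bilaterally.

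**The case against.** **The rule is prespecified and determinate.** SAP 7.3 recognises that rescue confounds the efficacy measures and names one method. Nothing in the plan promises that failures will be non-responders. This is a fair defence of carry-forward for mean scores. It does not remove the contradiction of one subject being labelled a failure and counted as improved.

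**Good pre-rescue scores are unlikely.** Protocol 13.1 and 13.2 tie rescue to increased or persistent polyposis with symptoms that make the subject seek it. SAP 6.4 takes the score from the unscheduled visit at which steroids are prescribed. Both points stand and will reduce the number affected. But persistence is compatible with partial improvement, as the examples show, and the SAP 6.4 rule does not mention visits preceding surgery.

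**Disclosure.** Interventions are tabulated and concomitant medications listed, so steroid rescue could be traced by subject, but no planned summary says which responders were rescued. The baseline summary gives the minimum obstruction score, which would settle (b) if it is 2; otherwise it does not give the number below 2. The table mock-ups appear in our text as a heading only and may add more.

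**The heading of the list might supply the missing condition.** A programmer could add an improvement requirement to the below-2.0 row. The row does not state one, and its literal reading is the natural one to code.

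A reader might also infer three stronger points, which the documents do not support:

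- *Carry-forward does not reach responder rates,* because they are listed in SAP 4.3 while SAP 7.3 says "All efficacy endpoints will be presented as intervention-adjusted values". This is strained: SAP 7.3 applies its method to the analyses, names the scores from which response is derived, and SAP 7.4 treats efficacy and other endpoints together.
- *The grade after a Day 90 polypectomy enters the Day 90 row.* Protocol 11.3 requires that grading to decide on repeat placement. SAP 7.3 carries forward scores from before the intervention, which largely settles the matter.
- *The measure of being indicated for repeat surgery is also faulty.* It is openly a score-based status, assessed "on each side at Day 90 and at Day 180", and claims no improvement.

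**Conclusion.** The point holds in two limited parts. As written, SAP 7.3 and 7.4 allow a treatment failure to be reported as a responder at later visits through Day 180, and one of the ten responder rows can be met without any improvement.

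The size is unknown and may be zero for both. The 60% rate and the values of k and m are assumptions; only the 2 points per subject follows from the plan. For k up to 5, the shifted rates stay inside the interval around the assumed rate. Relative to counting failures as non-responders, the SAP's rates can only be equal or higher. Relative to observed post-rescue scores they could be lower, so a general claim of inflation would go too far.

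The endpoints are descriptive, have no success criterion and lie outside the safety objective. Priority is low, but the correction is cheap.

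**What to change.** - In SAP 7.4, state that a subject with treatment failure is a non-responder in every responder row at visits after the intervention. Keep the carry-forward version as a sensitivity analysis.
- Optionally, extend the unscheduled-visit rule in SAP 6.4 to visits preceding polypectomy or repeat sinus surgery. Protocol 11.3 already requires both questionnaires and endoscopic grading at unscheduled visits.
- Compute the below-2.0 row among subjects with a baseline score of 2 or more. Alternatively, relabel it as a status row, outside the improvement heading, with the baseline proportion beside it.

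The changes should precede database lock, because SAP 6.5 treats analyses designed later as post hoc.

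Cost: SAP wording and derivation code; no new data. Responder rates under (a) will print the same or lower. Restricting the below-2.0 row may shrink its denominator and widen its interval; relabelling it avoids that.
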